2. OBJECTIVES

The primary objective of this study is as follows:

- To characterize the long term (i.e., 96 weeks of follow up) bone safety profile of open-label Tenofovir DF treatment in CHB-infected adolescents. This includes prospectively evaluating and comparing the bone mineral density (BMD) change between CHB- infected adolescents 12 to < 18 years of age treated with Tenofovir DF in European treatment centers who are assigned to one of two schedules for renal and bone laboratory monitoring and BMD measurement. Primary study endpoint will be the percent changes in BMD from Baseline through study Week 96.

The secondary objectives of this study are as follows:

- To document all serious adverse drug reactions (SADR) and all renal- and bone-related adverse events (AEs), including renal and bone laboratory abnormalities
- To determine the time to diagnosis of renal and bone AEs and document the resulting patient management and outcome(s)
- To assess the clinical management and outcomes of renal- and bone-related \geq Grade 3 laboratory markers and clinical SAEs.
- To assess the efficacy and tolerability of Tenofovir DF in adolescents with CHB infection
- To assess the use of oral vitamin D, calcium and phosphate supplementation and explore the association between supplement use and rates of bone and renal AEs
- To describe the demographics and disease characteristics of adolescents with CHB infection treated with Tenofovir DF.

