6.2. Pre-treatment Assessments

6.2.1. Screening Visit

Subjects will be screened within 30 days before assignment to determine eligibility for participation in the study. The following will be performed and documented at screening:

- 1) Obtain written informed consent
- 2) Obtain medical history
- 3) Complete physical examination including, vital signs, body weight, and height

- 4) Screen for pregnancy (serum screen) and contraceptive use
- 5) Conduct preliminary liver chemistry tests (ALT, ALP, AST, total and direct bilirubin, total protein, albumin, GGT, LDH, CK), serum renal chemistry (glucose, creatinine, creatinine clearance (calculated), magnesium, bicarbonate, chloride, potassium, sodium) and urinalysis (glucose, protein, creatinine, phosphate, bicarbonate, blood, calcium) (to be averaged with Baseline renal chemistry values), fasting required
- 6) HBV serology (HBeAg and HBsAg; anti-HBe and anti-HBs (if Ag negative))

Subjects meeting all of the inclusion criteria and none of the exclusion criteria will return to the clinic within 30 days after screening for commencement into the study.

From the time of obtaining informed consent through the first administration of Tenofovir DF, record all renal and bone AEs and any SAEs (not limited to bone or renal) on the adverse events case report form (CRF/eCRF). All other untoward medical occurrences observed during the screening period, including exacerbation or changes in medical history are to be captured on the medical history CRF/eCRF. See Section 7 Adverse Events and Toxicity Management for additional details.

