7.2.2. Assessment of Severity

Severity should be recorded and graded according to the GSI Grading Scale for Severity of Adverse Events and Laboratory Abnormalities ([Appendix 4](#)). For AEs associated with laboratory abnormalities, the event should be graded on the basis of the clinical severity in the context of the underlying conditions; this may or may not be in agreement with the grading of the laboratory abnormality.

7.3. Investigator Requirements and Instructions for Reporting Adverse Events and Serious Adverse Events to Gilead

Requirements for collection prior to Tenofovir DF initiation:

After informed consent, but prior to initiation of Tenofovir DF, the following types of events should be reported on the case report form (CRF/eCRF): all SAEs and AEs related to protocol-mandated procedures.

Adverse Events

Following initiation of Tenofovir DF, collect all bone and renal AEs, regardless of cause or relationship, until 30 days after last administration of Tenofovir DF must be reported to the CRF/eCRF database as instructed.

All bone and renal AEs should be followed up until resolution or until the adverse event is stable, if possible. Gilead Sciences may request that certain AEs be followed beyond the protocol defined follow up period.

Serious Adverse Events

All bone and renal SAEs, regardless of cause or relationship, that occurs after the subject first consents to participate in the study (i.e., signing the informed consent) and throughout the duration of the study, including the protocol-required post treatment follow-up period, must be reported to the CRF/eCRF database and Gilead Drug Safety and Public Health (DSPH) as instructed. This also includes any bone and renal SAEs resulting from protocol-associated procedures performed after informed consent is signed.

Any SAEs and deaths that occur after the post treatment follow-up visit but within 30-days of the last dose of Tenofovir DF, regardless of causality, should also be reported.

Investigators are not obligated to actively seek bone and renal SAEs after the protocol defined follow up period, however, if the investigator learns of any SAEs that occur after study participation has concluded and the event is deemed relevant to the use of Tenofovir DF, he/she should promptly document and report the event to Gilead DSPH.

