- All bone and renal AEs and (S)ADRs and all SAEs (not limited to bone and renal events) will be recorded in the CRF/eCRF database within the timelines outlined in the CRF/eCRF completion guideline.
- At the time of study start, SAEs will be reported using a paper serious adverse event reporting form. During the study conduct, sites may transition to an electronic SAE (eSAE) system. Gilead will notify sites in writing and provide training and account information prior to implementing an eSAE system.

Serious Adverse Event Paper Reporting Process

- All pre-specified SAEs will be recorded on the serious adverse event report form and submitted by faxing or emailing the report form within 24 hours of the investigator's knowledge of the event to the attention of Gilead DSPH or to the designated CRO.

CRO (TBD)

Contacts (TBD)

Gilead Sciences DSPH
Representative:

[contact]
E-mail: [contact]

Electronic Serious Adverse Event (eSAE) Reporting Process

- Site personnel record all SAE data in the eCRF database and from there transmit the SAE information to Gilead DSPH within 24 hours of the investigator's knowledge of the event. Detailed instructions can be found in the eCRF completion guidelines.

- If for any reason it is not possible to record the SAE information electronically, i.e, the eCRF database is not functioning, record the SAE on the paper serious adverse event reporting form and submit within 24 hours as described above.
- As soon as it is possible to do so, any SAE reported via paper must be transcribed into the eCRF Database according to instructions in the eCRF completion guidelines.
- If an SAE has been reported via a paper form because the eCRF database has been locked, no further action is necessary.
- For fatal or life-threatening events, copies of hospital case reports, autopsy reports, and other documents are also to be submitted by e-mail or fax when requested and applicable. Transmission of such documents should occur without personal subject identification, maintaining the traceability of a document to the subject identifiers.
- Additional information may be requested to ensure the timely completion of accurate safety reports.
- Any medications necessary for treatment of the SAE must be recorded onto the concomitant medication section of the subject's CRF/eCRF and the event description section of the SAE form.

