8.6.2. Adverse Events

Clinical and laboratory AEs will be coded using the Medical Dictionary for Regulatory Activities (MedDRA). System Organ Class (SOC), High-Level Group Term (HLGT), High-Level Term (HLT), Preferred Term (PT), and Lower-Level Term (LLT) will be attached to the clinical database.

Events will be summarized on the basis of the date of onset for the event. A treatment-emergent adverse event will be defined as any adverse event that begins on or after the date of first dose up to the date of last dose of Tenofovir DF plus 30 days.

Summaries (number and percentage of subjects) of treatment-emergent AEs related to **bone or renal SOCs** (hierarchically ordered by SOC, HLT, and PT) will be provided by treatment group:

- all treatment-emergent bone or renal AEs,
- all related treatment-emergent bone or renal AEs,
- combined Grade 2, 3, and 4 treatment-emergent bone or renal AEs,
- combined Grade 3 and 4 treatment-emergent bone or renal AEs,
- combined Grade 2, 3, and 4 related treatment-emergent bone or renal AEs,
- combined Grade 3 and 4 related treatment-emergent bone or renal AEs,
- all AEs that caused permanent discontinuation from Tenofovir DF,
- all AEs that caused permanent discontinuation from study,
- all AEs that caused change in dose or temporary interruption of Tenofovir DF,
- all serious AEs (all SOCs, i.e., not limited to bone or renal SOCs), and
- all serious bone or renal related AEs.

Events will be summarized based on the date of onset for the event. A treatment-emergent adverse event will be defined as any adverse event that begins on or after the date of first dose of Tenofovir DF. Events that occur prior to the first dose of Tenofovir DF or after the last dose of Tenofovir DF will be included in data listings.

PPD

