7.1.6. Summaries of Adverse Events and Deaths

A brief summary of AEs will show, by monitoring group, the number and percentage of subjects who (1) had any treatment-emergent AE, (2) had any Grade 3 or 4 treatment-emergent AE, (3) had any Grade 2, 3 or 4 treatment-emergent AE, (4) had any treatment-emergent treatment-related AE, (5) had any Grade 3 or 4 treatment-emergent treatment-related AE, (6) had any Grade 2, 3 or 4 treatment-emergent treatment-related AE, (7) had any treatment-emergent SAE, (8) had any treatment-emergent treatment-related SAE, (9) permanently discontinued from TDF due to an AE, and (10) died during study.

Summaries (number and percentage of subjects) of adverse events (by SOC and PT) will be provided by monitoring group using the safety analysis set as follows:

- All treatment-emergent bone or renal AEs
- All TDF-related treatment-emergent bone or renal AEs
- Combined Grade 3 and 4 treatment-emergent bone or renal AEs
- Combined Grade 2, 3 and 4 treatment-emergent bone or renal AEs
- Combined Grade 3 and 4 treatment-emergent treatment-related bone or renal AEs
- Combined Grade 2, 3 and 4 treatment-emergent treatment-related bone or renal AEs
- All treatment-emergent serious AEs
- All treatment-emergent treatment-related SAEs

- All treatment-emergent AEs that caused permanent discontinuation from TDF
- All treatment-emergent AEs that caused change in dose or temporary interruption of TDF
- Deaths
- All AEs recorded between screening and first dose of TDF

For final analyses, summaries will be provided by monitoring group and overall TDF.

Summaries and data listings will use the Safety Analysis Set.

Events will be summarized based on the date of onset for the event, according to the definition of treatment emergent in Section 7.1.5. Non-treatment emergent events, including those prior to the first dose date of TDF, will be included in data listings.

Multiple events will be counted once only per subject in each summary. For data presentation, SOC will be ordered alphabetically, with PT sorted by decreasing total frequency. For summaries by severity grade, the most severe event will be selected.

In addition to the by-monitoring group summaries, data listings will be provided for the following:

- All AEs (with a variable indicating whether the event is treatment-emergent)
- SAEs (including deaths)
- AEs leading to discontinuation of TDF
- Subjects experiencing pregnancy during the study

PPD

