19.3.2	Treatment-Emergent Adverse Events Related to TDF	Grade 3 or 4 Bone or Renal Adverse Events	SAS
19.4	Treatment-Emergent Adverse Events	Leading to Permanent TDF Discontinuation	SAS
19.5	Treatment-Emergent Adverse Events	Leading to Change in Dose or Temporary Interruption of TDF	SAS
19.6	Treatment-Emergent Renal Adverse Events – Clinical Management and Outcomes Summary		SAS
19.7	Treatment-Emergent Bone-related Adverse Events – Clinical Management and Outcomes Summary		SAS
19.8	Treatment-Emergent Bone-related Adverse Events – Oral supplement use summary		SAS
19.9	Treatment-Emergent Serious Adverse Events		SAS
19.10	Treatment-Emergent Serious Adverse Events Related to TDF		SAS
20	Treatment-Emergent Adverse Events Occurring with >= 5% Incidence in Any Monitoring Group		SAS

Table Number	Title	Title	Analysis Set
21.1	Calcium (mg/dL) and Change from Baseline		SAS
21.2	Phosphorus (mg/dL) and Change from Baseline		SAS
21.3.1	Creatinine (mg/dL) and Change from Baseline		SAS
21.3.2	Creatinine Clearance (mL/min/1.73m ²) and Change from Baseline	Based on Schwartz	SAS
21.3.3	Creatinine Clearance (mL/min) and Change from Baseline	Based on Cockcroft-Gault	SAS
22.1	N-telopeptides (nmol BCE/L) and Change from Baseline		SAS
22.2	C-telopeptides (ng/mL) and Change from Baseline		SAS
22.3	Serum Osteocalcin (ng/mL) and Change from Baseline		SAS
22.4	Bone-Specific Alkaline Phosphatase (µg/L) and Change from Baseline		SAS
22.5	Serum PTH (pg/mL) and Change from Baseline		SAS
22.6	Vitamin D Level (25-hydroxy) (ng/mL) and Change from Baseline		SAS
23.1	Treatment-Emergent	Laboratory Abnormalities by Grade	SAS
23.2	Treatment-Emergent	Laboratory Abnormalities	SAS
23.3	Treatment-Emergent	Grade 3 or Grade 4 Laboratory Abnormalities	SAS
23.4	Treatment-Emergent	Marked Laboratory Abnormalities	SAS
24	Hepatic and Renal Related Abnormalities	Treatment-Emergent	SAS
25	On-Treatment ALT Flare and post treatment Exacerbation of Hepatitis		SAS
26.1	Cumulative Incidence of At Least a 4% Decrease from Baseline in Spine Bone Mineral Density (g/cm ²) by Week		SAS
26.2	Percent Change from Baseline in Spine Bone Mineral Density (g/cm ²) by Week	Categorical Summaries	SAS
26.3	Z-Scores for Spine Bone Mineral Density (g/cm ²) and Change from Baseline by Week	Categorical Summaries	SAS

Table Number	Title	Title	Analysis Set
27.1	Cumulative Incidence of At Least a 4% Decrease from Baseline in Whole Body Bone Mineral Density (g/cm ²) by Week		SAS

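### SAP 7.1.6 and Tables 19.4, 19.5 and 20 present adverse events as unrestricted, although the protocol collects non-serious clinical events only if they concern bone or kidney

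*SAP*

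**What the plan says.** **Collection.** Once drug has started, protocol 7.3 tells sites to "collect all bone and renal AEs, regardless of cause or relationship, until 30 days after last administration of Tenofovir DF". The same section states what enters the database: "All bone and renal AEs and (S)ADRs and all SAEs (not limited to bone and renal events) will be recorded in the CRF/eCRF database". The screening rule in 6.2.1 has the same shape ("record all renal and bone AEs and any SAEs (not limited to bone or renal"). The visit lists in 6.3.2 and 6.4.1 to 6.4.6 ask for a review of bone and renal AEs only. Protocol 7.1.3 adds laboratory or imaging abnormalities of any kind that need intervention or change dosing.

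**Protocol analysis.** Section 8.6.2 lists the AE summaries under a lead-in limited to bone or renal SOCs. One item is "all AEs that caused permanent discontinuation from Tenofovir DF". Only the serious-AE item is expressly opened to every SOC.

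**SAP analysis.** Section 7.1.6 has no such lead-in. Its overall summary counts subjects with any treatment-emergent AE, with Grade 2–4 or Grade 3–4 AEs, and with related AEs (items 1–6), and those who stopped drug because of an AE (item 9). In the list that follows, six bullets name bone or renal. The bullet "All treatment-emergent AEs that caused permanent discontinuation from TDF" and the one on dose change or interruption do not. In Appendix 3, Tables 19.4 and 19.5 carry no limit, and Table 20 is titled "Treatment-Emergent Adverse Events Occurring with >= 5% Incidence in Any Monitoring Group". SAP 7.8 says the protocol's safety analysis is unaltered.

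**Objective.** A secondary objective is "To assess the efficacy and tolerability of Tenofovir DF in adolescents with CHB infection". SAP 2.1 keeps a description of tolerability in the final analysis despite early closure.

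**The concern.** A table of AEs that stopped drug, or of AEs reaching 5%, is normally read as covering every organ system. Here most organ systems are absent from the numerator by design unless the event was serious or was a qualifying laboratory or imaging finding. A low or zero count could therefore reflect the collection rule and be mistaken for good tolerability in adolescents.

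The discontinuation and interruption tables are the most exposed. Protocol 3.5 and 6.6 allow drug to be stopped for toxicity without limiting the organ system, and 7.5.2 and 7.5.3 address drug changes for related Grade 3 and 4 clinical events in general. The protocol thus foresees drug changes for events that 7.3 does not send to the AE database. Such a stop could appear among the disposition reasons (SAP 4.2) but not in Table 19.4, and two tables of one report would then disagree.

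**Working it through.** The plan gives no figure on this point to reproduce, so the check is mainly a comparison of passages.

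**1. What is collected against what is reported**

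| Event type | Called for by the protocol? | Outputs with no bone/renal limit |
|---|---|---|
| Bone or renal AE | Yes (7.3) | Counted |
| SAE, any system | Yes (7.3) | Counted |
| Laboratory or imaging abnormality needing intervention or changing dosing | Yes (7.1.3) | Counted |
| Other non-serious clinical AE, including one that stops drug | No | Implied by the text or title, but not in the data |

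**2. Direction.** The recorded events are a subset of those that occurred, so a count of subjects from the database is at most the true count. Any error is downward.

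**3. Where the SAP conflicts with itself.** Items 1–6 of 7.1.6 are unrestricted, but the overall summary they describe is Table 19.1, subtitled bone or renal in Appendix 3. Section 7.1.6 promises a listing of all AEs, whereas Listing 15.1 is limited to bone or renal AEs. Tables 19.4, 19.5 and 20 have no restriction in the text or the title.

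**4. Where the SAP departs from the protocol.** The bone-or-renal lead-in of protocol 8.6.2 is absent from SAP 7.1.6, and SAP 7.8 does not report its removal.

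**5. The 5% cut-off in Table 20.** SAP 1.4 gives 15 subjects per group. One subject is 1/15 = 6.7%, which is above 5%, so every recorded term qualifies. At the planned 50 per group, 1/50 = 2% and 2/50 = 4% fall below the cut-off and 3/50 = 6% passes, so it would have selected something.

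**6. Illustration for Table 19.4.** The rate of stopping drug for an uncollected AE is not in the documents. Call it q and assume 1% to 5%. The chance that at least one such stop is missed among 30 subjects is 1 − (1 − q)^30:
- q = 1%: 1 − 0.99^30 = 26%
- q = 3%: 1 − 0.97^30 = 60%
- q = 5%: 1 − 0.95^30 = 79%

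This shows only that a low rate could still matter with 30 subjects. It does not estimate how many stops were missed.

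**The case against.** The strongest reply is that this is a labelling gap in an openly targeted study. Much of that stands.

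- Limiting collection to bone and renal events is a legitimate choice for a post-authorization bone and renal safety study, and both groups share the rule and the drug. The point concerns absolute AE burden, not the comparison of groups.
- The overall summary is already subtitled bone or renal in Table 19.1, so its reader would see the limit. What remains there is a mismatch between text and title.
- A reader might infer from "all AEs that caused permanent discontinuation from Tenofovir DF" that the protocol itself plans an all-system discontinuation table. It does not, because that bullet sits under the bone-or-renal lead-in.
- SAEs and deaths cover all systems, dosing-related laboratory findings are recorded, and Tables 23.1 to 25 report laboratory abnormalities and ALT flares. Reasons for stopping drug are a secondary endpoint and are summarized under SAP 4.2.
- A reader might infer that other non-serious events are counted as exactly zero. That is too absolute. The reference to (S)ADRs in 7.3 can be read more widely, although 7.2.1 uses that label to classify renal or bone AEs. Protocol 7.6.2.2 asks for clinical sequelae of special situations, and the AE row in Appendix 2 reads wider than 7.3. These passages make recording variable between sites; they do not make it complete.
- Parts of SAP 7.1.6 and 7.1.7 are redacted and may contain text on AE scope.

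None of this puts a limit on Tables 19.4, 19.5 and 20 or restores the missing lead-in.

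**Conclusion.** The point holds as a mismatch between what the protocol collects and how the SAP labels it. The text of items 1–6 and 9 of SAP 7.1.6, and Tables 19.4, 19.5 and 20, present restricted data as all AEs. They can only understate non-serious events outside bone and kidney.

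The documents do not allow the size to be determined. A reader might infer that a large share of the 30 subjects drops out of the any-AE count. Assuming that 30% to 80% had an uncollected event gives 0.30 × 30 = 9 to 0.80 × 30 = 24 subjects. That range has no source in the documents, it ignores that subjects with a recorded bone or renal AE or an SAE are still counted, and it concerns a summary whose table is already subtitled.

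The failure of the 5% cut-off is certain at 15 per group, but it is a minor and separate consequence of early closure. The conclusion assumes that sites followed 7.3 and that the redacted text does not define the scope differently. The correction is worth making before reporting because it is cheap and bears directly on the tolerability statement.

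**What to change.** 1. **SAP 7.1.6 text.** Restrict items 1–6 to bone or renal AEs, to match Table 19.1, and make the listing of AEs agree with Listing 15.1. Title or footnote item 9 and Tables 19.4, 19.5 and 20 as covering bone/renal AEs, all SAEs, and laboratory or imaging abnormalities recorded under protocol 7.1.3. Correct 7.8 so that it no longer implies that the scope was carried over unchanged.
2. **Reconciliation.** Check Table 19.4 against the disposition reasons, and Tables 19.4 and 19.5 against source AE records, which protocol 3.6 and 8.12.5 require to hold all AEs. Disposition does not show temporary interruptions, so Table 19.5 depends on the source records. Count or footnote any stop or interruption due to another AE.
3. **Table 20.** Drop the 5% cut-off.
4. **Report.** Keep the objective as written, and state that the tolerability conclusion covers only bone/renal AEs, SAEs and recorded events leading to drug change.

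Recording every AE that led to a drug change, through 7.3 and the CRF, would have been the better design. SAP 2.1 puts the last visit in April 2018, so that amendment is now moot.

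The cost is wording in the SAP and table shells, a small reconciliation for 30 subjects, and a narrower tolerability statement.

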7.1.7. Additional Analysis of Adverse Events

PPD

7.2. Laboratory Evaluations

Selected laboratory data (using conventional units) will be summarized by the observed data and change over time. Missing laboratory results for safety summaries will not be imputed. In all cases for laboratory evaluations, no inferential statistics will be computed.

Glomerular filtration rate (estimated creatinine clearance) will be calculated via statistical programming at each visit

(a) using Schwartz formula for subjects ages 12–18 years (ie, 12 to < 19) as follows:

$$\text{Schwartz formula (mL/min/1.73 m}^2\text{)} = k \times L/\text{Scr}$$

k is a proportionality constant,

k=0.55 for adolescent females 12-18 years old; and

k=0.70 for adolescent males 12-18 years old

L is height in centimeters (cm); and

Scr is serum creatinine (mg/dL)

(b) using Cockcroft-Gault equation for age ≥ 12 years as follows:

$$\frac{(140 - \text{age in years}) (\text{body weight [kg]})}{(72) (\text{serum creatinine [mg/dl]})}$$

[Note: multiply estimated rate by 0.85 for women; use actual body weight]

Creatinine clearance (CLcr) summaries will be provided by Schwartz and Cockcroft-Gault separately.

Summaries and data listings will use the Safety Analysis Set. For subjects who discontinue prior to the final week for the given analysis, all on-treatment laboratory data collected on or before the date of last dose + 7 days will be included in tabular summaries. Laboratory data prior to the first dose date of TDF will be included in data listings.

Summaries of laboratory data will be provided for the safety analysis set. No inferential statistics will be generated.

